## RESEARCH OBJECTIVES

The use of patient-specific cutting guides for total knee joint replacement is being developed and introduced to clinical practice by a number of orthopaedic device companies. Each system differs in the way in which the cutting guides are designed, the material which they are made from, the alignment philosophy and the radiological information on which they are based (e.g. X-ray, CT, MRI).

The overall goal of this study is to assess the impact of a new surgical technique developed by Stryker on the functional outcome of participants undergoing primary total knee joint replacement.

The repeatability in placing the cutting guides relies on the reference points used in the design of the block, and the ability of the surgeon to position it on the diseased joint surfaces of the knee without the availability of traditional alignment jigs (femoral intra-medullary rod, tibial extra- or intra-medullary alignment guide). Hence, the first objective of this study is to quantify the reproducibility of this new technique by assessing cutting guide position using a repeated-measures methodology. The results will be described as a standard error of measurement.

Early reports indicate that improved post-operative functional outcomes may result from the use of this new technology when used in combination with particular designs of total knee joint prosthetic components (Howell et al, 2008; Spencer et al, 2009). The second objective is to assess and quantify such changes in the short-term (6

months) post-operative period. Potential benefits may be seen in the general quality of life experienced by participants, reduced pain levels, and specific improvements in activities of daily living affected by knee function. Other parameters related to the procedure, such as operating time, blood loss and length of stay in hospital will also be assessed to determine if perceived benefits with the use of this new surgical technique can be realised in routine clinical practice. Comparison of the study findings will be made to published literature on the clinical outcomes of total knee replacement (e.g. Kolisek et al, 2007; Matziolis et al, 2007; Harwin et al, 2008).

In addition, a cadaver study is being planned to further explore the precision analysis including quantification of intra- and inter-observer variation in placement of the cutting guides. Subsequent clinical studies such as randomised, controlled trials (RCTs) are envisaged to provide higher levels of evidence. The results of the case series outlined in this proposal will allow future studies to be designed in a sound manner, ensuring patient numbers and study design are sufficient to provide statistically-significant outcomes.

#### **4.0 NUMBER OF PARTICIPANTS**

Group A: Six investigators will recruit a minimum of 5 cases per investigator and a maximum of 60 cases in total.

Group B: Four hospitals and five investigators will recruit a total of 100 cases.

Extension Study: Participants from Group B will be invited; a maximum of 100 cases will be included.

#### **5.0 LENGTH OF STUDY AND PATIENT PARTICIPATION**

The enrolment period for Group A is expected to be 3 months or until the required sample size is reached. For Group B, individual study participants will be seen for at least 6 months after surgery. The enrolment period is expected to be 6 months. Therefore it is anticipated that the entire study will take approximately 1.5 years to complete.

At the completion of the 6 month follow-up visit patients will receive an invite to continue participation in the study via enrollment into the Extension Study. Patients

will be required to give informed consent and will need to meet the Extension study inclusion and exclusion criteria (see sections 6.3 and 6.4).

## **6.0 PATIENT SELECTION CRITERIA**

Each Investigator is responsible for evaluating each patient against the following criteria and assuring that the patient meets the requirements to be enrolled in this clinical investigation. Each patient enrolled in this investigation must meet each of the following inclusion criteria and have none of the exclusion criteria. Any patient enrolled in this study who does not meet the inclusion and exclusion criteria will be considered a protocol deviation.

### **6.1 Inclusion Criteria**

- The patient is a male or non-pregnant female between the ages of 50-90.
- The patient requires a primary total knee replacement and is indicated for computer-assisted surgery.
- The patient has a primary diagnosis of osteoarthritis (OA).
- The patient has intact collateral ligaments.
- The patient is able to undergo MRI scanning of the affected limb.
- The patient has signed the study specific, HREC-approved, Informed Consent document.
- The patient is willing and able to comply with the specified pre-operative and post-operative clinical and radiographic evaluations.

### **6.2 Exclusion Criteria**

- The patient has a history of total, unicompartmental reconstruction or fusion of the affected joint.
- Patient has had a high tibial osteotomy or femoral osteotomy.
- The patient is morbidly obese ( $BMI \geq 40$ ).
- The patient has a deformity which will require the use of stems, wedges or augments in conjunction with the Triathlon Total Knee System.
- The patient has a varus/valgus malalignment  $\geq 15^\circ$  (relative to mechanical axis).
- The patient has a fixed flexion deformity  $\geq 15^\circ$ .

- The patient has a neuromuscular or neurosensory deficiency, which would limit the ability to assess the performance of the device.
- The patient has a systemic or metabolic disorder leading to progressive bone deterioration.
- The patient is immunologically suppressed or receiving steroids in excess of normal physiological requirements.
- Patient has a cognitive impairment, an intellectual disability or a mental illness.
- The patient is pregnant.
- The patient has metal hardware present in the region of the hip, knee or ankle (as this is known to create geometrical distortion in the region of the implant).
- The patient has any known contraindications for undergoing assessment by MRI (e.g. ferrous implants, metallic clips, magnetically activated implanted devices such as cardiac pacemakers, etc).

**6.3 Extension Study: Inclusion Criteria (applicable to patients electing to continue participation in the Extension study).**

- Patient was enrolled in TriShapeMatch-10 study and completed 3 month follow-up visit.
- Patient is willing and able to give informed consent to participate in the study.
- Patient is willing and able to comply with the specified clinical and radiographic evaluations.

**6.4 Extension Study: Exclusion Criteria (applicable to patients electing to continue participation in the Extension study).**

- Patient no longer has the Triathlon Custom Fit Knee featuring Stryker ShapeMatch *in situ*, including patients that have had revision surgery.
- Patient has a cognitive impairment, an intellectual disability or a mental illness.
- Patient no longer resides in a geographical location that would reasonably permit clinic visits at protocol specified intervals.

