All implanted prosthetic components (Stryker Triathlon Primary Total Knee System) used in this study are TGA approved for sale and use in Australia. This study was originally to be undertaken via the Clinical Trial Notification (CTN) Scheme of the Therapeutic Goods Administration (Therapeutic Goods Act, 1989); however the ShapeMatch® Cutting Guides are now also listed on the Australian Register of Therapeutic Goods (ARTG) for sale and use in Australia.

This study will adhere to all relevant requirement and guidelines in relation to the conduct of clinical trials, including the Declaration of Helsinki (Appendix 5) and ICH Good Clinical Practice Guidelines, as implemented in Australia (Appendix 6).

An Extension Study will be undertaken to follow Group B patients who consent to continued follow-up. These patients will be followed out to 5 years post-surgery with follow-up visits at 12 months, 2 years and 5 years in order to collect longer term data on radiographic and patient outcomes.

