### **Visit Windows**

Definition – Since it is not always possible for subjects to come in for a study visit on the exact date, most protocols allow a certain time period before or after the calendar date; this is known as the visit window. If a subject is not seen during the visit window, that visit will be regarded as a missed visit. Visit windows are calculated in reference to the baseline date, which is the surgery date (intra-op) for this study.

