#### Part B: Functional outcome sub-study

EVALUATION	History/ Pre-Op	Intra-Op	6 week	3 MO	6MO
Demographics	✓				
Medical History	✓				
MRI	✓				
Surgical Details		✓			
International Knee Society Score	✓			✓	✓
KOOS	✓		✓	✓	✓
SF-12 v2	✓		✓	✓	✓
VAS Pain	✓		✓	✓	✓
AP and ML X-rays	✓		✓		
Perth CT Protocol				✓	✓*

The visit windows for this study are:

- Pre-Op = Within 2 months before the date of surgery
- Intra-op = Baseline time point
- 6 Weeks = +/- 2 weeks
- 3 Months = +/- 1 month (+/- 6 weeks for CT only – except WA site)
- 6 Months = +/- 1 month(+/- 6 weeks for \*CT WA site Only and X-ray only)

Extension Phase:

EVALUATION	12 month follow-up	2 year follow-up	5 year follow-up
Demographics	✓		
BMI	✓	✓	✓
Medical History Review	✓		
Surgical Details	✓		
Knee Society Score	✓	✓	✓
KOOS	✓	✓	✓
SF-12 v 2	✓	✓	✓
VAS Pain	✓	✓	✓
Forgotten Joint Score	✓	✓	✓
Anteroposterior (A/P) and Lateral Knee Radiographs	✓		✓
Long leg (A/P) weight bearing x-ray	✓		✓
Adverse Events	✓	✓	✓

The visit windows for this study are:

- 12 Months = +/- 3 months
- 2 years = +/- 3 months
- 5 years = +/- 4 months

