#### **Group B**

Howell et al (2008) reported improvements in post-operative Knee Society Score resulting from the use of ShapeMatch® Cutting Guides for total knee replacement. A comparison of these results with those reported by Matziolis et al (2007) when using computer-assisted surgery for total knee replacement suggests that such differences may be clinically significant. An improvement of 15 points in the Knee Society Score (from 150 to 165 points, out of a maximum of 200) with a standard deviation of 35 can be assumed as representing a clinical significant improvement. Using these figures,

with 80% power, power analysis indicates that 87 patients per group are required. This does assume comparison of two independent groups with the t-test. Allowing for patient drop out, a minimum of 100 cases is recommended.

All 100 cases will be invited to participate in the Extension Study.

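### Section 6.3 makes a completed 3-month visit a condition of Extension entry although no Extension endpoint uses it, and section 5.0 does not say whether a patient who misses 6 months is still invited

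*Combined protocol and SAP*

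**What the plan says.** Five places bear on who enters the Extension.

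- **Section 6.3 (Extension inclusion):** "Patient was enrolled in TriShapeMatch-10 study and completed 3 month follow-up visit". This is the only eligibility criterion tied to an early visit. The other two concern consent and willingness to comply with evaluations.
- **Section 5.0:** "At the completion of the 6 month follow-up visit patients will receive an invite to continue participation in the study". It adds that patients "will be required to give informed consent and will need to meet the Extension study inclusion and exclusion criteria (see sections 6.3 and 6.4").
- **Section 12.1 (Group B):** "All 100 cases will be invited to participate in the Extension Study".
- **Section 4.0:** "Participants from Group B will be invited; a maximum of 100 cases will be included".
- **Section 1.0:** "An Extension Study will be undertaken to follow Group B patients who consent to continued follow-up".

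The Visit Windows paragraph in section 1.0 defines a missed visit strictly: "If a subject is not seen during the visit window, that visit will be regarded as a missed visit". The 3-month visit window is plus or minus 1 month. The CT has its own window of plus or minus 6 weeks, except at the WA site, whose CT appears from the schedule to fall at 6 months.

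Section 3.0 sets the Extension objectives: clinical and radiographic outcomes at 12 months, 2 years and 5 years, then revision rate, device-related adverse events and reoperation rates. Section 12.2 compares revisions with national registry figures at the same three times.

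**The concern.** Attendance at 3 months is observed after treatment and may be related to outcome. A patient may stay away because of a complication, dissatisfaction or care sought elsewhere, or because the knee is doing so well that a visit seems pointless. When attendance is an entry condition, one missed window removes all 12-month, 2-year and 5-year data from a patient who has had the study procedure, unless the patient is lost for some other reason anyway.

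The Extension has no control group and at most 100 cases, so it depends on the cohort representing those operated on. One revision among 100 patients is 1 percentage point, so losing even a few patients selectively can matter in the registry comparison.

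There is also a practical problem. Section 5.0 gives a site no instruction for a patient who attended at 3 months and missed 6 months. Sites may handle such patients differently.

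**Working it through.** **1. The plan's own figure.** The pool of 100 comes from section 12.1: difference 15 points, SD 35, 80% power, two-group t-test. Significance is 0.05 (section 12.2), taken as two-sided. The t-test calculation gives 86.44 per group, rounded up to the stated 87. Going from 87 to 100 implies 1 − 87/100 = 13% dropout. The figure reproduces, and the present point does not depend on it.

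**2. The passages applied to two patients.**

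| Patient | 6.3 | 5.0 | 12.1 | Result |
|---|---|---|---|---|
| Missed 3 months, attended 6 months | Not eligible | Invited, then referred to 6.3 and 6.4 | Invited | Barred by 6.3 |
| Attended 3 months, missed 6 months | Meets the visit criterion | Invitation timed at a visit that did not occur | Invited | Unresolved |

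The first exclusion comes from 6.3 alone. Aligning the other sections with 6.3 would tidy the wording without changing who is lost.

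**3. Is the 3-month visit needed for the Extension?** The Extension schedule contains no CT. It lists demographics, medical history review and surgical details at 12 months, and section 11.0 says that review covers events from surgery to the 12-month visit. Nothing in the Extension objectives, schedule or analysis calls for a 3-month value.

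**4. Size of the loss.** The documents give no missed-visit rate, so p = 5% to 10% per visit is an assumption.

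- 6.3 alone: 100 × p = 5 to 10 patients.
- Both visits treated as conditions, misses independent: 100 × (1 − (1 − p)²) = 100 × (1 − 0.95²) = 9.75, to 100 × (1 − 0.90²) = 19. If the same patients miss both visits, this falls back to 5 to 10.

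**5. Effect on a mean score.** If the barred fraction p would score d points lower than the rest, the mean among those entered exceeds the full-cohort mean by p × d. Take d = 10 to 15 Knee Society points (assumption).

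- 6.3 alone: 0.05 × 10 = 0.5, to 0.10 × 15 = 1.5 points.
- Both visits: 0.0975 × 10 = 0.98, to 0.19 × 15 = 2.85 points.

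If the barred patients would score higher, the sign reverses.

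**6. Effect on precision.** The 95% half-width is 1.96 × 35/√n, carrying over the Group B planning SD: 6.86 at n = 100, 7.04 at 95, 7.23 at 90 and 7.62 at 81. The loss of precision is small, so selection is the main issue.

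**The case against.** The strongest defence is that the sections can be read together. Section 6.3, with 6.4, is the eligibility rule; section 5.0 gives the time of invitation and defers to those criteria; section 12.1 describes who is invited. Being invited and then screened out is ordinary. This stands, and it limits the point in several ways.

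- A reader might infer three rival entry rules. The documents contain one eligibility rule, one invitation time and one invitation pool, imperfectly aligned.
- A reader might infer that missing any early visit bars a patient. Missing 6 weeks bars nobody. Missing 6 months bars a patient only if section 5.0's timing is read as a condition, which the text does not say.
- A reader might therefore take 10 to 19 lost patients as the expected figure. It needs that two-visit reading as well as the assumed rates.
- A reader might assume that long-term results would be flattered. The documents do not establish the direction, since patients may also skip visits because they are well.

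Some patients who miss visits would be lost anyway through death, withdrawal, relocation, revision or refusal (sections 6.4 and 17.2), so the incremental loss is smaller than the calculated one. Patients already revised are excluded by 6.4 in any case; only later events are at issue here. The 15-point difference is also a Group B planning figure, and the Extension analysis is mainly descriptive.

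The 3-month visit does carry the Group B CT endpoint on implant position, which is a possible reason for the criterion. The documents do not give that reason, and it fits poorly. Section 6.3 asks for the visit, not the CT. Outside WA, a CT taken between 1 month and 6 weeks from the 3-month date is valid while the visit counts as missed. At the WA site the 3-month visit does not appear to secure the CT at all.

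**Conclusion.** The point holds for the 3-month criterion. It is an attendance condition applied after treatment, with no stated purpose and no Extension endpoint behind it, and it excludes patients whom sections 1.0, 4.0 and 12.1 would include. The silence of section 5.0 on patients who miss 6 months is a separate gap that needs a sentence.

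The size is modest. At an assumed 5% to 10% missing the 3-month visit, section 6.3 alone bars up to 5 to 10 of 100, or about 0.5 to 1.5 Knee Society points if those patients would score 10 to 15 lower. The larger figures, 10 to 19 patients and about 1 to 2.9 points, apply only if the 6-month visit is also enforced as a condition and misses are independent. At the assumed rates, all of these are upper bounds before refusals, withdrawals and 6.4 exclusions. The case for change is that the selection is avoidable at little cost, and that patients never entered cannot later be followed prospectively.

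**What to change.** Make three wording changes in one amendment.

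1. **Section 6.3:** replace the 3-month-visit clause with a requirement that the patient underwent Group B surgery with the ShapeMatch guides and has not withdrawn consent. Leave the Extension consent criterion, the compliance criterion and section 6.4 as they are.
2. **Section 5.0:** state that every such Group B patient is invited at the 6-month time point whether or not the visit takes place, by post or telephone if needed.
3. **Section 12.1:** describe the same invitation pool in the same terms.

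If the sponsor prefers to keep the 3-month condition, the protocol should give the reason and say whether the 6-month visit is a condition or only the time of invitation.

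The cost is the amendment and a few letters or calls. The downside is that a few Extension patients will lack a 3-month or 6-month value.

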**7.0 STUDY DESIGN**

**Group A:** This is a repeatability study of ShapeMatch® patient-specific cutting guides designed for participants undergoing total knee arthroplasty with the Triathlon® Total

Knee System (Stryker Orthopaedics, Mahwah NJ, USA) and Stryker eNact Knee Navigation System (Stryker Navigation, Kalamazoo MI, USA). Participants will undergo pre-operative assessment using MRI of the affected limb according to the scan protocol (see Appendix 2 for example). At the time of surgery, a repeated-measures methodology will be implemented in which the position of the femoral and tibial cutting guides will be measured using the Navigation system. The same surgeon will position each cutting guide a total of 3 times for each patient. Multiple participants will be assessed by each surgeon. No bone resections will take place using the patient-specific cutting guides. After the study-specific measurements have been taken, the total knee procedure will resume using the Navigation system and associated instruments being used to prepare the distal femur and tibia prior to implantation of the Triathlon® total knee components. No post-operative evaluations will be undertaken as part of this sub-study. However, participants will have routine visits, as per the investigators' standard-of-care for such participants.

Approximately 30 participants (5 per investigator) up to a maximum of 60 participants will contribute to this sub-study.

**Group B:** This is a consecutive sample survey of participants undergoing total knee arthroplasty with the Triathlon® Total Knee System (Stryker Orthopaedics, Mahwah, NJ USA) utilizing ShapeMatch® patient-specific cutting guides to prepare the bony resections on the distal femur and proximal tibia. Health status and functional outcome measures will be recorded to quantify functional status of subjects before surgery and at each follow-up interval.

Participants suitable for primary total knee arthroplasty and indicated for computer-assisted surgery will be booked for surgery. Recruitment will be subject to gaining suitable informed consent from the patient.

Participants will undergo pre-operative assessment using MRI of the affected limb according to the scan protocol (Appendix 2).

Appropriate total knee replacement components from the Stryker Triathlon® Total Knee System will be used.

All patients undergoing total knee replacement routinely have anterior-posterior (AP) and medio-lateral (ML) X-rays taken of the affected knee pre-operatively and post-operatively. In addition, a more comprehensive assessment of total knee replacement component position and orientation will be obtained using the Perth CT protocol (Appendix 3; Chauhan et al, 2004).

Demographic details, diagnosis, coexistent disease and concomitant medications will be collected preoperatively and adverse events will be collected during and after surgery. Surgeons will monitor participants following surgery as per their standard of care for such participants.

Participants will follow the standard postoperative rehabilitation program established by the investigator at the study site.

### *Subjects*

Subjects will be screened using the inclusion and exclusion criteria, and enrolled from the clinic after informed consent has been obtained. Their personal information and co-morbidities will be recorded from the chart and functional status will be assessed using the International Knee Society Score, SF-12 v2, Knee Osteoarthritis Outcome Score (KOOS), and Pain Visual Analog Scale. All information will be kept strictly confidential.

Demographic details and body mass index will be collected preoperatively and complications will be collected after surgery.

## **8.0 DEVICE DESCRIPTION**

### **8.1 Device Trade Name**

The instruments used to resect the distal femur and proximal tibia as part of this study will be referred to as the **Stryker ShapeMatch® Cutting Guides**. These devices are single-use, patient-specific instruments, approved for use in Australia by the Therapeutic Goods Administration.

The prosthetic components to be implanted as part of this study will collectively be referred to as the **Stryker Triathlon Primary Total Knee System**. Within this system, various individual implants of different designs, sizes and thicknesses are included, including:

- CR Femoral Component – Cemented
- CR Femoral Cementless Component – Beaded with Peri-Apatite
- PS Femoral Component – Cemented
- PS Femoral Cementless Component – Beaded with Peri-Apatite
- Primary Tibial Baseplate – Cemented
- Primary Tibial Baseplate – Beaded with Peri-Apatite
- CR Tibial Insert – X3
- CS Tibial Insert – X3
- PS Tibial Insert – X3

The **Stryker Triathlon Primary Total Knee System** is a commercially available, TGA (Therapeutic Goods Administration) listed device, and has been approved for sale and use throughout Australia.

In addition, the **Stryker eNact Knee Navigation System**, comprising of computer hardware and software and associated instrumentation, will be used for intra-operative assessment of implant and limb position. This system is a commercially available, TGA (Therapeutic Goods Administration) listed device, and has been approved for sale and use throughout Australia.

